R01 DA036550
Behavioral Effects of Pregabalin and Cannabis
NCT01511640
10/28/2020

Study Protocol

Adult men and women, aged 18-50, who could speak and read English were recruited from the local community using flyers, social media, research participant registries, outreach activities, paid digital and print advertisements and referrals. Potential participants were required to report daily or near-daily cannabis use (i.e., at least 25 days per month of use as defined in Budney et al., 2007) and provide a urine sample positive for cannabis use and negative for other recent illicit substance use. Individuals with a history of serious physical disease or non-personality psychiatric disorders according to DSM-IV (computerized Structured Clinical Interview for DSM-IV, Psychmanager, Multi-Health Systems Inc., North Tonawanda, NY; 300 mg/day pregabalin group) or DSM-5 (online SAGE-SR, Telesage Inc., Chapel Hill, NC; 450 mg/day pregabalin group) criteria, other than disordered use (i.e., abuse and/or dependence for DSM-IV and use disorder for DSM-5) of nicotine and/or cannabis, were excluded from participating. Further exclusion criteria included seeking or currently receiving treatment for drug use, desire to reduce drug use or abstain from use independent of the study procedures, medical screening outcomes outside normal ranges deemed clinically significant by the study physician, history of, or current, angioedema, seizure disorder, use of prescription medications other than hormonal contraceptives or antibiotics, and pregnancy in women. Participants were also excluded for having first-degree family history of either cardiovascular disease that resulted in premature death or seizure disorder.

This study used a placebo-controlled, double-blind, pregabalin- and cannabis-dose counterbalanced, mixed within- and between-subjects design. Participants were enrolled as outpatients. Two active doses of pregabalin, 300 and 450 mg/day, were tested in separate groups of participants (i.e., active pregabalin dose [300 and 450 mg/day] was a between-subjects factor). In the 300 mg/day group, participants attended two practice sessions prior to completing two 11-day

pregabalin maintenance phases (150 mg administered twice per day for a total daily dose of 300 mg, or placebo). Each maintenance phase began on a Monday and ended on the Thursday of the following week, with a 10-day inter-phase interval. Each phase consisted of seven maintenance-only days (Monday through the following Sunday) and four experimental sessions (Monday through Thursday). During experimental sessions, maintenance continued, and participants completed two 2-day blocks of sampling and self-administration sessions to determine the reinforcing effects of cannabis (0 and 5.9% THC). In this way, cannabis concentration (0 and 5.9%) THC and pregabalin dose (0 and 300 mg/day) were within-subjects factors. In the 450 mg/day group, participants received placebo and 450 mg of pregabalin per day (divided into two daily doses of 225 mg), and the maintenance phase lasted 15 days (Thursday through Thursday), with a 6-day inter-phase interval.

Participants were required to abstain from illicit drugs other than cannabis throughout participation. Daily urine tests to assess recent drug use and pregnancy were negative throughout. Participants were also asked to avoid any over-the-counter medication, with the exception of non-steroidal anti-inflammatory analgesics. On maintenance-only days, participants were administered the first of the two daily pregabalin doses and were given a “take-home” dose. Participants did not report to the laboratory on weekends. On Fridays, participants received additional take-home capsules. At the end of each maintenance phase, participants were tapered off of pregabalin. Practice and experimental (i.e., sampling and self-administration) sessions were conducted on weekdays and lasted 6.5 h. Participants were asked to refrain from food, caffeine, alcohol, tobacco and cannabis use prior to arrival. At intake, a breath sample was obtained to assess recent alcohol use. Participants also completed a field sobriety test (Toland & Green, 1991) and were observed by trained research staff for cannabis intoxication (e.g., bloodshot, glassy eyes). Participants were required to consume a low-fat snack at intake. Participants who smoked tobacco cigarettes were allowed to smoke a single tobacco cigarette upon arrival to the laboratory to avoid testing under conditions of nicotine withdrawal. They were not allowed to smoke again until the session had ended. Participants were reassessed at the end of the session for possible intoxication and/or impairment using the field

sobriety test prior to release. In addition, participants were required to report no drug effects. The first practice session duplicated a sampling session and the second a self-administration session. Participants smoked un-blinded placebo cannabis cigarettes to become acquainted with the paced smoking procedure. On the practice self-administration session, participants were required to work to receive the maximum number of puffs (8) to familiarize them with the response requirements. Sampling Sessions were conducted to familiarize participants with the effects of the cannabis they could work for in a subsequent session. Participants were instructed to pay attention to the effects of the cannabis, as they would be given the opportunity to work to receive puffs from the same cannabis condition in the next session. During self-administration sessions, immediately after maintenance dosing, participants completed a self-administration task to earn puffs of cannabis sampled the day prior and/or an alternative monetary reinforcer (\$0.50), which were concurrently available on independent progressive-ratio (PR) schedules. A maximum of 8 reinforcers could be earned (e.g., 8 puffs of cannabis, \$4 or some combination of cannabis puffs and money), and participants were required to make a total of 8 choices. The initial response requirement for each reinforcer was 400 responses (i.e., mouse clicks). The completion of a response requirement for a given reinforcer (i.e., cannabis puffs or money) increased the response requirement for that reinforcer by 200. Once the task was complete, participants self-administered the number of puffs earned using the paced smoking procedure. Cannabis cigarettes (0 and 5.9% THC) were provided by the National Institute on Drug Abuse. Pregabalin (0, 150 and 225 mg) was administered in one opaque capsule containing commercially available Lyrica® (Pfizer, Inc., New York, NY) twice per day. Doses were based on those recommended for neuropathic pain and seizures (i.e., 150-600 mg/day). Doses were escalated across the initial maintenance days up to the target dose, based on the Product Information recommendations. Prior to drug administration, heart rate was assessed. If heart rate exceeded 100 bpm, drug administration would have been withheld, but this did not occur.

Data Analyses

To account for the correlation among repeated measures, generalized estimating equations with random participant effect were used to fit a linear model for the primary outcome in both groups. Fixed effects for pregabalin and cannabis, as well as their interaction, were used as predictors. Tests were two-sided and utilized a 5% significance level. Significant interactions were followed with post-hoc pair-wise comparisons. Analyses were conducted in SAS version 9.4.

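### The plan does not say which error each effect is tested against: a single pooled error or uncorrected empirical standard errors, and neither holds the 5% level in general

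*Combined protocol and SAP*

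**What the plan says.** The design paragraphs of the Study Protocol describe a 2×2 layout within each participant. For the lower-dose group, "cannabis concentration (0 and 5.9%) THC and pregabalin dose (0 and 300 mg/day) were within-subjects factors"; the 450 mg/day group compares placebo with its own active dose in the same way. Pregabalin changes between two maintenance phases. Cannabis changes inside a phase, where "participants completed two 2-day blocks of sampling and self-administration sessions to determine the reinforcing effects of cannabis". Each participant therefore contributes four cells.

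The Data Analyses section states that "generalized estimating equations with random participant effect were used to fit a linear model for the primary outcome in both groups". The model terms are given as "Fixed effects for pregabalin and cannabis, as well as their interaction, were used as predictors", and "Tests were two-sided and utilized a 5% significance level". On follow-up tests it says: "Significant interactions were followed with post-hoc pair-wise comparisons". On software it says only that "Analyses were conducted in SAS version 9.4".

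The section does not state the working correlation, whether standard errors are model-based or empirical (sandwich), any small-sample correction, the SAS procedure, or the number of participants.

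**The concern.** GEE is a marginal method with a working correlation and has no random effects, so the sentence mixes two methods. The only dependence it names is one effect per participant. Taken literally, that makes a participant's four results equally variable and equally correlated.

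The design gives reasons to doubt this. Participants may differ in how strongly they prefer 5.9% to 0% THC, from one phase to the other, or in how pregabalin changes that preference. Each effect then has its own error. One participant effect replaces the three errors by their average, so some tests are too strict and others too lenient.

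The interaction matters most. It asks whether pregabalin changes the reinforcing effect of cannabis, and its significance is the only stated trigger for the pair-wise comparisons.

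**Working it through.** The documents give no sample size, variance or power figure, so there is nothing of the plan's own to reproduce. The 2×2 layout, the three model terms and the two-sided 5% level come from the documents. I assume complete data, one result per cell, N participants in the fit (8 to 24) and a residual variance of 1.

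**Step 1: own error and pooled error.** For each participant, form three contrasts of the four cells with coefficients ±1/2: pregabalin (P), cannabis (C) and interaction (I). Call their variances λP, λC and λI.

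- Own-error test: mean contrast divided by √(λ̂/N), where λ̂ is the estimate of that contrast's own variance, on N−1 df.
- Random-intercept or model-based exchangeable fit: one error with expectation (λP + λC + λI)/3, on 3(N−1) df.
- SE ratio, pooled to correct: √(average λ / own λ). It equals 1 for all three effects only if the three λ are equal.

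**Step 2: put in variance components.** Let sp be the participant-by-phase SD per level and sc the participant-by-cannabis SD per level. Pregabalin changes only with phase, so sp also carries differences in response to pregabalin. Then λP = 1 + 2sp², λC = 1 + 2sc², λI = 1, and the pooled error is 1 + (2/3)(sp² + sc²).

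For sc = 1, sp = 0.5: λP = 1.5, λC = 3, λI = 1, and pooled = 1 + (2/3)(1.25) = 1.833. The SE ratios are:

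- pregabalin √(1.833/1.5) = 1.11
- cannabis √(1.833/3) = 0.78
- interaction √(1.833/1) = 1.35

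Simulated behaviour of the pooled-error test follows. The effect size is set so that the own-error interaction test has 80% power.

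| Assumed variation | λP, λC, λI | SE ratio P / C / I | Actual level of nominal 5% test | Interaction power at N = 10, 16, 24 |
|---|---|---|---|---|
| none | 1, 1, 1 | 1 / 1 / 1 | 5% for all | 86, 83, 82% |
| sc = 1, sp = 0.5 | 1.5, 3, 1 | 1.11 / 0.78 / 1.35 | I about 1%, C about 12% | 65, 61, 59% |
| sp = 1, sc = 0 | 3, 1, 1 | 0.75 / 1.29 / 1.29 | P about 14% | 69, 65, 64% |
| sp = 1, sc = 0.5 | 3, 1.5, 1 | 0.78 / 1.11 / 1.35 | P about 12%, I about 1% | 65, 61, 60% |
| interaction only | 1, 1, 3 | 1.29 / 1.29 / 0.75 | I about 14% | not meaningful, level not held |

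The last row lies outside the sp/sc model. It is there because nothing in the design rules it out. The own-error test held about 5% in every setting.

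**Step 3: the empirical-variance reading.** With complete data, the sandwich standard error of each contrast is its own-error standard error times √((N−1)/N), whatever the working correlation. Referred to the normal distribution, the actual level is P(|t with N−1 df| > 1.96·√((N−1)/N)).

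- N = 8: about 11%
- N = 10: 9.6%
- N = 12: 8.7%
- N = 24: 6.8%

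A GEE score test was slightly conservative instead: about 4.3 to 4.5% at N = 12, with interaction power 0.77 to 0.78.

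**Step 4: one simulated data set, N = 14.** It shows that the choice changes the answer on the same data (order P / C / I):

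- random-intercept model: 0.500 / 0.500 / 1.000
- GEE, model-based: 0.502 / 0.502 / 1.004
- own error: 0.487 / 0.647 / 0.613
- GEE, empirical: 0.470 / 0.624 / 0.590

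The first two carry the same pooled error for every effect. The last is the own error times √(13/14).

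**The case against.** The strongest reply is that the sentence names GEE, and GEE is usually reported with empirical standard errors. Under that reading each effect keeps its own error even with an exchangeable working correlation, so pooling does not arise. This stands, and it means the pooled error cannot be asserted as fact. It does not clear the plan, because the uncorrected Wald test then errs the other way, towards too many rejections.

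Second, the harm depends on variances that the documents do not give. With no participant-by-effect variation the pooled test is valid and slightly more powerful. That also stands.

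Third, under the sp/sc model the interaction can never have the largest error, so its loss of power is built into that model. This is correct: variation mainly in the interaction reverses the direction. The two harms also need different settings. At sc = 1, sp = 0.5 the pregabalin test is conservative (ratio 1.11), and the 12 to 14% false-positive rate for pregabalin needs sp = 1 with sc between 0 and 0.5.

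A reader might infer that the interaction test was definitely underpowered, or that all the standard errors are wrong. The documents do not support this. They leave open the type of standard error, N, the variances and therefore the direction of any error.

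**Conclusion.** The point holds in conditional form. The stated analysis permits two readings, and neither holds the 5% level in general at the sample sizes assumed here. A random-intercept or model-based fit tests all three effects against one averaged error. With sc = 1 and sp = 0.5 the interaction test then runs at about 1%, with 59 to 65% power instead of 80% for N from 24 to 10. With variation mainly in the interaction, its level rises to about 14%. An empirical-variance fit avoids pooling, but its uncorrected Wald tests reject a true null about 9 to 10% of the time at N = 10 and 6.5 to 7% at N = 24.

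These sizes rest on assumed N, assumed variance components, complete data and a continuous outcome. Equal variation in all three effects is the one case in which pooling does no harm, and the plan gives no reason to expect it. Because the fix guards against both readings at little cost, this is a cheap improvement and not only a request for missing detail.

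**What to change.** In Data Analyses, replace the reference to a random effect for participant with an analysis that tests each effect, and each pair-wise comparison, against its own within-participant variation on N−1 df. Either of these forms will do; with complete data they agree:

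- **Per-participant contrasts.** The interaction is the 5.9%-minus-0% difference on pregabalin minus the same difference on placebo, tested with a one-sample t test. Each pair-wise comparison uses its own paired difference.
- **An unstructured 4×4 covariance** over the four cells in a SAS mixed model, with a stated small-sample df method.

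Keeping GEE with empirical standard errors is an acceptable alternative if the small-sample correction is named. In every case, state the procedure, the correlation structure, the type of standard error and N. If the completed analysis used a pooled error or an uncorrected Wald test, rerun it.

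The cost is a sentence or two of text and a few lines of SAS, with no new data. The statistical price is df: N−1 per test instead of 3(N−1). If there is no participant-by-effect variation, interaction power is about 6 points lower at N = 10 (80% against 86%) and about 2 points lower at N = 24 (80% against 82%).

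### Does leaving the primary outcome unnamed leave the pregabalin-by-cannabis interaction test open?

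*Combined protocol and SAP*

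**What the plan says.** The Study Protocol describes sessions meant to determine how reinforcing cannabis is at 0 and 5.9% THC. In the self-administration session, participants make 8 required choices between cannabis puffs and $0.50, each on its own progressive-ratio schedule. The first ratio is 400 mouse clicks. Completing a ratio "increased the response requirement for that reinforcer by 200". Participants then smoke the puffs they have earned.

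The Data Analyses section states that generalized estimating equations were "used to fit a linear model for the primary outcome in both groups". On the model terms it says "Fixed effects for pregabalin and cannabis, as well as their interaction, were used as predictors", and on testing "Tests were two-sided and utilized a 5% significance level". It adds: "Significant interactions were followed with post-hoc pair-wise comparisons".

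Neither section attaches a variable to the primary outcome.

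**The concern.** The reinforcing effect of cannabis is a construct, and a progressive-ratio task can be scored in more than one way. Three candidates are puffs earned (0 to 8), the last cannabis ratio completed (breakpoint), and total clicks made for cannabis. Clicks are not a linear transform of puffs, so an effect that is additive in puffs becomes an interaction in clicks. A linear model's interaction term therefore depends on the score chosen.

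The interaction also decides whether pair-wise comparisons are run. If the score were chosen after looking at the data, that choice could settle whether the comparisons appear at all. A reader of this document alone cannot confirm which test was primary.

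**Working it through.** The document gives no sample size, power, effect size or standard deviation, so there is no planned figure to reproduce. The check uses the task schedule.

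**Inputs (Study Protocol):** first ratio 400 clicks; increment 200 for the reinforcer just earned; 8 required choices, so money choices = 8 - puffs.

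**Formulas for n cannabis puffs**

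- Clicks = 400n + 200·n(n-1)/2 = 300n + 100n². This assumes that every cannabis click belongs to a completed ratio.
- Breakpoint = 400 + 200(n-1) = 200 + 200n for n ≥ 1, and 0 for n = 0. The zero coding is an assumption; the document defines no breakpoint.

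| Puffs | 0 | 1 | 2 | 3 | 4 | 5 | 6 | 7 | 8 |
|---|---|---|---|---|---|---|---|---|---|
| Breakpoint | 0 | 400 | 600 | 800 | 1,000 | 1,200 | 1,400 | 1,600 | 1,800 |
| Clicks | 0 | 400 | 1,000 | 1,800 | 2,800 | 4,000 | 5,400 | 7,000 | 8,800 |

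**Interaction** = (pregabalin - placebo at 5.9% THC) - (pregabalin - placebo at 0% THC).

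- 3 to 2 at 0% and 6 to 5 at 5.9%: puffs (-1) - (-1) = 0; breakpoint (-200) - (-200) = 0; clicks (4,000 - 5,400) - (1,000 - 1,800) = -1,400 + 800 = -600.
- 1 to 0 and 6 to 5: puffs 0; breakpoint (-200) - (-400) = +200; clicks -1,400 + 400 = -1,000.
- 3 to 0 and 7 to 5: puffs (-2) - (-3) = +1; clicks (4,000 - 7,000) - (0 - 1,800) = -3,000 + 1,800 = -1,200, the opposite sign.

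Across all 9⁴ = 6,561 four-cell profiles, puffs and clicks differ in interaction sign in 336 + 36 + 140 = 512 (7.8%). These are respectively zero on puffs only, zero on clicks only, and opposite signs. The profiles are weighted equally, so this is not a probability. Puffs and breakpoint never have opposite signs. With no zero-puff cell, the breakpoint interaction is exactly 200 times the puff interaction. The real contrast is puffs against clicks.

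**Illustrative simulations.** Sample sizes, means and spreads are assumed, and a t-test on each participant's interaction contrast stands in for the GEE.

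- *Sequential-choice model*, n = 12 and 20, 4,000 trials per cell, mean drop of 1 puff at both THC levels. The puff interaction rejects in about 5%. Clicks reject in 7-17% (means 3 to 2 and 6 to 5) or 8-29% (2 to 1 and 6 to 5). Puffs and clicks disagree on significance in 5-16% and 8-28%. With no pregabalin effect, every measure rejects in 4-6% and they disagree in 2-4%.
- *Rounded normal model*, scores limited to 0-8, SD 1 puff between and within participants, 4,000 runs:

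| Latent means (0%: placebo, pregabalin; 5.9%: placebo, pregabalin) | N | Puffs reject | Breakpoint rejects | Clicks reject | Puffs and clicks disagree |
|---|---|---|---|---|---|
| 2.5, 1.5; 6, 5 | 10 | 5.2% | 5.6% | 13.6% | 12.2% |
| 2.5, 1.5; 6, 5 | 16 | 5.6% | 6.4% | 20.0% | 19.2% |
| 2.5, 1.5; 6, 5 | 30 | 5.8% | 6.7% | 31.5% | 30.4% |
| 1.5, 0.5; 5.5, 4.5 | 10 | 5.7% | 4.9% | 20.1% | 15.5% |
| 1.5, 0.5; 5.5, 4.5 | 16 | 7.5% | 4.9% | 31.9% | 25.8% |
| 1.5, 0.5; 5.5, 4.5 | 30 | 10.0% | 5.8% | 53.8% | 45.0% |

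In the lower three rows the floor at zero shortens the drop at 0% THC, so the puff scale itself carries some interaction.

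A repeat of the sequential-choice model, in the scenarios with an effect, gave power for the pregabalin main effect of 64-99% on puffs and 59-98% on clicks. Whether pregabalin changes self-administration overall therefore depends little on the score.

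**The case for a change.** The strongest case for acting is simple. A primary outcome should be stated, one sentence would do it, and the text leaves the reader to infer it. The text is also in the past tense, so it cannot show when the measure was fixed. The schedule makes the choice matter for the interaction, and the interaction controls the follow-up comparisons.

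The omission and the arithmetic stand. Three further steps do not.

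- The alternatives are not the document's. It never mentions breakpoint, and clicks appear only as the unit of responding. With 8 compulsory choices nobody stops responding, and breakpoint departs from puffs only through the assumed coding of zero.
- An outcome not stated here has not been shown to be left open. The section refers to a single primary outcome, and this is a short summary of a completed study. When the measure was fixed cannot be judged from it either way.
- Reporting the interaction on all three scores is a preference, conditional on the measure not having been chosen beforehand. It is not a better analysis. Clicks can be derived from puffs only if participants could not switch part-way through a ratio, which the text does not settle.

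**Conclusion.** No change to the plan follows. The document leaves out a definition that an analyst would fill sensibly: puffs earned out of 8 is the only result of the task it describes, and the stated linear model, terms and two-sided 5% test apply to it directly. On that reading there is one interaction test per active-dose group if the groups are fitted separately, and the rule for pair-wise comparisons is clear.

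If clicks had been the outcome, the interaction could differ by the amounts shown, such as 0 puffs against -600 clicks. The differing rejection rates arise when pregabalin has an effect: an additive effect on one scale is a genuine interaction on the other. With no effect, the simulated error rate is 4-6% on every measure. The algebra rests on the stated schedule and on completed ratios. The simulated rates rest on assumed inputs and only illustrate the point. A sentence naming the measure would help readers, but it would clarify the reporting and would not alter the stated analysis.

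### The model has no phase or block term although both dose orders were counterbalanced; an order effect, if present, would lower rejection rates, or bias estimates if completed orders are unequal

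*Combined protocol and SAP*

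**What the plan says.** The Study Protocol section describes a "pregabalin- and cannabis-dose counterbalanced, mixed within- and between-subjects design". For the 300 mg/day group there are two maintenance phases, one active and one placebo: "Each maintenance phase began on a Monday and ended on the Thursday of the following week, with a 10-day inter-phase interval". Within each phase "participants completed two 2-day blocks of sampling and self-administration sessions", one block per cannabis concentration. For the 450 mg/day group "the maintenance phase lasted 15 days (Thursday through Thursday), with a 6-day inter-phase interval". The two-block structure is set out only under the 300 mg/day group; I assume it for the other.

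Data Analyses fits a linear model by generalized estimating equations, described as having a random participant effect, to each group. On its terms it says: "Fixed effects for pregabalin and cannabis, as well as their interaction, were used as predictors". Pairwise comparisons follow a significant interaction. The documents do not state a phase, block or sequence term, a check for order effects, the number completing each order, whether cannabis order was the same or reversed between a participant's two phases, or whether standard errors are robust or model-based.

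**The concern.** Counterbalancing is used because order might matter. It removes an additive order effect from the estimate, but only when equal numbers complete each order. Even then it does not remove the effect from the residual. A model without order terms therefore counts a systematic shift as noise.

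Two things are at stake. With equal orders, a real pregabalin or cannabis effect is easier to miss. With unequal orders, part of the shift is read as a treatment effect, in a direction that the reader cannot tell. In both groups the phases start 21 days apart (11 + 10 and 15 + 6 days), which leaves room for drift in response to the task or in outside circumstances.

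**Working it through.** The documents give no power, sample size or effect figure to reproduce. All sizes below rest on assumed inputs: 10 to 20 participants per group, and a phase shift of k = 0.25, 0.5 or 1 times the SD of the within-person pregabalin difference (k = 1 is extreme). Type I error and power come from simulation (at least 20,000 runs per setting) and, where there is no phase effect, from the noncentral t distribution. The true effect is set so that the phase-adjusted t-test has 80% power with equal orders.

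**1. Where a shift lands.** With pregabalin effect δ and phase shift π, each participant's pregabalin difference is δ + π + error in one order and δ - π + error in the other. A phase shift cancels from the interaction estimate. A block shift b enters the cannabis contrast as ±b if cannabis order is the same in both phases. If it is reversed, b enters the interaction as ±2b and the pregabalin effect at each THC level as ±b.

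**2. Equal orders, bias.** The ±π terms average to zero, so the estimate is unbiased and its true variance is unchanged.

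**3. Equal orders, paired standard error.** With the SD of the difference set to 1, the expected sample variance is 1 + k²·n/(n-1). At n = 16 and k = 0.5 this is 1 + 0.25 × 16/15 = 1.267, so the estimated SE is √(1.267/16) = 0.281 against a true 0.250. At k = 0.25 and 1 it is 0.258 and 0.359.

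| k | Paired t, type I | Paired t, power (80% with phase) | Uncorrected robust z, type I, n = 10-20 |
|---|---|---|---|
| 0.25 | about 4.5% | about 79% | roughly 6-9% |
| 0.5 | about 3% | about 73% | roughly 4-7% |
| 1 | about 0.6% | about 50% | roughly 1-2% |

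The robust z-test starts above 5% at these sample sizes (8.7% at n = 12 with no order effect). The omission pulls it down, but not necessarily below 5%.

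**4. Equal orders, pooled error.** In a random-participant model with one residual variance, the pregabalin difference averaged over two cannabis levels has variance σ²/2 + σ²/2 = σ², so k = 1 is a shift of one residual SD. The shift is spread over three within-person contrasts, so SEs are inflated by about √(1 + k²/3): 1.01, 1.04 and 1.155 at k = 0.25, 0.5 and 1. The residual is shared, so all three tests are affected. At n = 12 and k = 1, type I error is about 2.3% for pregabalin, cannabis and the interaction alike.

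**5. Unequal orders.** Bias = π(n1-n2)/(n1+n2). Paired t-test, phase omitted, k = 0.5:

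| Split | Bias (SD) | Type I | Power, by sign of shift | Power with phase |
|---|---|---|---|---|
| 8/6 | 2/14 × 0.5 = 0.07 | about 3.5% | 80% or 64% | 79% |
| 10/6 | 4/16 × 0.5 = 0.125 | about 4.8% | 86% or 56% | 77% |

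At 12/4 the bias is 8/16 × 0.5 = 0.25 SD and type I error about 11.6%. The same formula applies to a block shift on whichever contrast it loads on.

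**The case against.** The strongest reply is that the harm is hypothetical. Counterbalancing is the design's protection, and no imbalance or order effect is shown. Several features make an order effect less likely. "Potential participants were required to report daily or near-daily cannabis use", so the drug was not novel. Before each self-administration session participants sampled that cannabis and were told that "they would be given the opportunity to work to receive puffs from the same cannabis condition in the next session". There were also practice sessions. At k = 0.25 with equal orders the loss is only 1 to 2 points of power, and at a 12/4 split with no phase effect, adding phase costs 12 points. All of this stands. It makes the point conditional, but it does not remove the case for a cheap adjustment.

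Three stronger readings are tempting, and the documents do not support them:

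- A reader might infer that the reported tests are conservative, below 5%. That depends on the variance method, which is not stated; an uncorrected robust z-test can stay above 5%.
- A reader might infer that a phase shift leaves the interaction untouched. That holds for its estimate, and for its test under robust or paired standard errors. Under pooled error the interaction test loses rejections too, and that test gates the pairwise comparisons.
- From "In the 300 mg/day group, participants attended two practice sessions prior to completing two 11-day" a reader might infer that the 450 mg/day group had no practice. Later paragraphs of the Study Protocol describe practice sessions without limiting them to one group.

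**Conclusion.** The omission is plain in the text, but its effect on this trial is unknown. If there is an additive order effect and completed orders are equal, estimates are unbiased and rejection rates fall. Under robust or paired standard errors this touches only the contrasts aliased with order; under pooled error it touches all three tests. On the assumed inputs a paired t-test loses about 1, 7 or 30 points of power at k = 0.25, 0.5 or 1. If completed orders are unequal, the affected estimate is biased by (n1-n2)/(n1+n2) times the shift. Mild imbalance at k = 0.5 does not raise paired-t type I error above 5%; marked imbalance does.

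A reader might go further and conclude that the results are biased or the analysis invalid. Nothing in the documents shows an order effect or unequal completion, so that does not follow. This is an adjustment that should be made, not a fatal flaw.

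**What to change.** In each group's model add phase (1 or 2) and block within phase (1 or 2) as fixed effects, with a test that is valid in small samples, for example a linear mixed model with Kenward-Roger degrees of freedom. Do not add the terms to an uncorrected robust z-test, whose type I error would be about 8 to 12% at n = 10 to 20. State the variance method. Report the adjusted contrasts beside the unadjusted ones, the number completing each pregabalin and cannabis order, and whether cannabis order was the same or reversed between phases.

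Data Analyses is written in the past tense, so this is a short re-analysis, using phase and block data that should already be on record. Each term uses one degree of freedom. If there is no phase effect, adding phase lowers power from 81.2% to 80.0% at n = 10 with equal orders, and by 0.4 and 0.2 points at n = 16 and 20. With unequal orders it falls from 80.6% to 79.2% at 8/6, from 80.4% to 77.4% at 10/6 and from 80.4% to 68.0% at 12/4. The last is the price of an estimate free of additive phase bias: its SE is ½√(1/12 + 1/4) = 0.289 against 1/√16 = 0.250.

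State the limits too: additive terms do not remove carryover or, in general, an effect confined to the first session.
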